Two questionnaires will be used to assess health-related quality of life: the EQ-5D-5L [40] and the Short Form 12 (SF-12) health survey [41]. The EQ-5D-5L provides a descriptive self-assessment of health in 5 dimensions: mobility, self-care, usual activities, pain/discomfort and anxiety/depression [40]. It is commonly used as a quality of life measure to conduct cost effectiveness analyses [42]. The EQ-5D-5L has a greater emphasis on physical than mental health, but has demonstrated the ability to capture changing anxiety severity [43]. The SF-12 survey is a reliable measure of functional health and is well-suited for this study, as it includes mental health items and has been shown to be acceptable for use as a screening tool for depressive disorders [44].

Cost-effectiveness

To conduct a health economic analysis, the study will collect data on health and social care service use, medication use and treatment costs, the implementation costs of Wysa, out of pocket medical expenses borne by patient and carers and productivity related costs such as work absence / time off work due illness. This data will be combined with the quality-of-life indicators to produce an assessment of the costs of adopting Wysa from the perspective of both the UK health and social care services and the wider society [45]. This analysis will also produce a budget impact model for each site that will be used to provide a final overall implementation strategy for more rapid adoption at other NHS sites and dissemination across the AHSN network in partnership with the new Integrated Care Systems. The team will also incorporate the environmental sustainability calculation in line with the Greener NHS agenda.

Table 6. Secondary Outcome Measurement

Secondary Outcome	Outcome Measure
Anxiety severity	
 Score on the GAD-7 [37]
Crisis identification	
 Number of users identified by the app for escalation of care compared to the number of patients in the control group who access A&E or out-of-hours services while waiting for treatment
Engagement	
 Uptake rates Dropout / 'did not attend' rates App usage data Qualitative feedback from semi-structured interviews
Acceptability	
 Qualitative feedback from semi-structured interviews Automated review questions periodically requested during general use of the tool

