8.3.1.2 Exclusion Criteria

- Patients ineligible for the standard IAPT care pathway;
- Patients with previous and current known major mental illness such as Schizophrenia, severe depression, any co-morbid neurological or neuro-psychiatric condition such as epilepsy;
- Patients with current psychosis or a history of psychotic symptoms within the last 6 months
- Patients with suicidal ideation;
- Patients scoring > 15 points on PHQ- 9;
- Patients scoring > 15 points on GAD- 7;
- Patients with significant cognitive disorders;
- Patients with noted neurodevelopmental conditions such as autism or ADHD;
- Patients previously diagnosed with a personality disorder;
- Patients who been under the care of CMHT or a specialised mental health services in the last 2 years;
- Patients who failed IAPT previously;

- Patients with referrals for specialist presentations of pre-existing, diagnosed conditions requiring a specialised assessment beyond the standard clinical pathway;
- Incapable of self-consent;
- In a dependent/unequal relationship with the research or care teams or any PPI representatives.

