8.3.2 Sampling

8.3.2.1 Sample Size

Approx 1100 eligible patients are seen per month at the IAPT in the CNWL NHS Foundation Trust. Preliminary work suggests that Wysa is associated with a mean clinical improvement in PHQ-9 of 5.84 (SD6.66) [28]. This study is powered to detect a clinically meaningful effect on the PHQ-9 scale [28]. Based on a SD of 6.6 and a 2:1 recruitment ratio (usual care: intervention) a sample size of 393 would allow detection of a difference in PHQ-9 of at least 2 points, with 80% power. Augmenting the sample size to 480 would allow for 20% attrition, whilst still maintaining sufficient power to detect clinically and statistically meaningful differences with a Type 1 error rate of 0.05. This inflated sample size would also allow for adjustment for stratification variables, gender, age, ethnicity, self-reported antidepressant use, and severity of depression.

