8.5 Data Analysis

8.5.1 Statistical Methods for Primary Outcome

Descriptive statistics will be used to characterise users, assess baseline comparability, and compare side effects. Primary comparisons between intervention and control groups will be conducted for primary and secondary outcomes. Primary analyses are designed with 80% power to detect a two-sided α of 0.05. All analyses will report 95% CI around estimate of effect. Comparative analyses will be conducted on an intention to treat basis, using linear or logistic regression, with adjustment for stratification variables.

We will explore missingness in our data, be that in relation to primary outcomes, follow-up data and in WYSA analytic information. The proportion of missing data will be explored and reported on descriptively. An hypothesised scenario, where patients remove themselves from the waiting list for treatment before the duration of follow-up may lead to missing data scenario. Currently, estimates

suggest that xxx% of our cohort will 'drop-off' waiting list before our primary endpoint. We will conduct exploratory sensitivity analyses in a complete case ('per protocol') cohort compared with the ITT analysis.

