Each of the study participants will be given a unique identifier. The primary key between unique ID and participant shall be stored securely for reference purposes and provided to the participant so that they can request that their data be withdrawn from the study. This can be requested at any point prior to data aggregation and will result in all of the patient's files and data being destroyed. Data collected in the study will be analysed using the unique identifiers rather than patient names. Data subject consent forms and primary research data will be retained for 10 years following

publication of the final study results. Study participants will have the option to retain their information within the WYSA app for their onward use or to reset their data at the completion of the study.

Follow-up interview sessions shall be audio recorded by [name] and his research team. The interviews will be transcribed by a transcription service with only reference to the unique identifier provided in the audio file for transcription (the audio file will be reviewed by the CI to ensure no identifying information is in the audio recording; if any is provided it will be edited out); the risk of identification of the interview sessions shall be very low due to this measure being taken. The original audio recording will be destroyed following transcription. Only the Academic CIs and their research staff will have access to research data. The transcription service will have access only to interview audio, following the controls previously mentioned.

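### Neither document says how a missing 3-month PHQ-9 enters the ITT regression, so the only planned missing-data check may compare the same people with themselves

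*Protocol*

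**What the plan says.** The primary outcome is the PHQ-9, collected at baseline and 3 months (Protocol 8.2.5.1 and 8.4.3.1). No trial visit between the two is scheduled.

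Protocol 8.5.1 sets the model: "Comparative analyses will be conducted on an intention to treat basis, using linear or logistic regression, with adjustment for stratification variables". On missing data it says "The proportion of missing data will be explored and reported on descriptively" and names one possible cause, that "patients remove themselves from the waiting list for treatment before the duration of follow-up may lead to missing data scenario". The expected size of that drop-off is an unfilled placeholder. The sensitivity analysis is "We will conduct exploratory sensitivity analyses in a complete case ('per protocol') cohort compared with the ITT analysis".

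Elsewhere:

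- Table 6 in Protocol 8.2.5.2 lists "Dropout / 'did not attend' rates" as an engagement measure.
- Protocol 8.3.2.1 says "Augmenting the sample size to 480 would allow for 20% attrition".
- Protocol 8.5.2 adds adjustment for baseline imbalance and subgroup and dose analyses, none of which addresses missing outcomes.
- The SPIRIT-AI checklist (Appendix 5), in its item on missing-data methods, refers only to section 8.5.
- The SAP (8 August 2023), under Statistical methods, gives linear regression for PHQ-9 and GAD-7 plus post hoc analyses by baseline score. It mentions neither ITT nor missing data.

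**The concern.** An ITT label says that people are analysed in the arm to which they were randomised. It does not say what happens to someone with no outcome. With a single follow-up score and no stated rule, a regression uses only people whose score is present. The ITT analysis would then be a complete case analysis under another name, and the planned comparison would hold no information about attrition.

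The label in the protocol also merges two different sets: people whose outcome was observed, and people who adhered to their allocation. Removing non-adherers as well would change the cohort, but any difference that followed would reflect adherence and not loss to follow-up.

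At stake is whether a reader of the result can tell how far it depends on who is missing. Someone who leaves the waiting list because of recovery or deterioration leaves for a reason related to the outcome. Loss could also differ by arm, because questionnaires reach participants through the app or through an online survey (Protocol 8.4.3.1) and participants know their allocation. The documents make this plausible; they do not establish it.

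**Working it through.** **1. The plan's own figures.** Protocol 8.3.2.1 gives a 2-point difference, 2:1 allocation, 80% power and 393 patients; 8.5.1 gives a two-sided 0.05 level. Total = 3 × 1.5 × (SD × (1.96 + 0.84)/2)², rounded up by arm. SD 6.6 gives 129 × 3 = 387. SD 6.66, also quoted in that section, gives 131 × 3 = 393. The stated size therefore reproduces. At 20% loss, 480 × 0.20 = 96 are missing and 384 remain, with unadjusted power of 79.9%.

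**2. The two analyses if missing scores are dropped.** The ITT regression uses the roughly 384 with a score. The complete case regression uses the same people and the same model, so the estimate is the same. Simulated trials confirmed this to rounding error.

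**3. How far missing outcomes would have to differ.** Let p1 and p0 be the missing fractions in the intervention and control arms. Let d1 and d0 be how much worse (higher PHQ-9) the missing patients are than the model assumes. Benefit is control minus intervention.

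- Estimate in all randomised = observed benefit − p1·d1 + p0·d0
- SE = residual SD × √(1/m1 + 1/m0), where m1 and m0 are the numbers analysed
- One-arm tipping shift = (observed benefit − 1.96·SE)/p1

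From the protocol: 480 randomised, SD 6.6, 2:1, 20% loss. Assumed: loss equal by arm, observed benefit 2.0, baseline correlation r = 0.5.

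Taking 6.6 as the SD of the 3-month score, residual SD = 6.6 × √(1 − 0.25) = 5.72. SE = 5.72 × √(1/128 + 1/256) = 0.619. The significance threshold is 1.96 × 0.619 = 1.213. The tipping shift is (2.0 − 1.213)/0.20 = **3.9 points**, with controls unshifted. If the arms shift in opposite directions it is 0.787/0.40 = 2.0 points each.

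The SAP gives the 2:1 ratio in the opposite direction from the protocol, and the two must be reconciled. With equal loss the result above is the same either way.

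**4. Which SD is 6.6?** Protocol 8.3.2.1 introduces 6.66 alongside a mean improvement, so 6.6 may be a change-score SD. With equal variances at both times, the residual SD is then 6.6 × √((1 + r)/2). Tipping shifts at 20% loss:

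| r (assumed) | 6.6 is the 3-month SD | 6.6 is a change SD |
|---|---|---|
| 0.3 | SE 0.682, shift 3.3 | SE 0.576, shift 4.4 |
| 0.5 | SE 0.619, shift 3.9 | SE 0.619, shift 3.9 |
| 0.7 | SE 0.510, shift 5.0 | SE 0.659, shift 3.5 |

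**5. Other assumed inputs, r = 0.5.**

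- 30% loss in both arms (112 and 224 analysed): SE 0.661, shift (2.0 − 1.296)/0.30 = **2.3**.
- 30% intervention and 15% control loss: 2.5 under the protocol's ratio, 2.6 under the SAP's.
- Observed benefit 1.5: (1.5 − 1.213)/0.20 = 1.4. Observed benefit 2.5: 6.4.
- SD of 5, since the criterion "Patients scoring > 15 points on PHQ- 9" narrows the baseline range: SE 0.469, shift (2.0 − 0.919)/0.20 = 5.4.

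**6. The case of no bias.** If p1 = p0 and d1 = d0, then − p1·d1 + p0·d0 = 0. Equal loss with equal shifts leaves the estimate unchanged.

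**The case against.** The strongest reply is that the text points away from dropping. Setting a complete case cohort against the ITT analysis makes sense only if the authors took ITT to include people outside that cohort. If the ITT model did impute, the comparison would say something. This stands as a reading: a reader might infer that the plan drops missing scores, or that the primary result is biased, and the documents support neither. What remains is that no imputation, weighting or other method is named in either document, so the comparison's value cannot be judged from the plan.

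Second, leaving the waiting list can happen in both arms, and equal loss with equal shifts does no harm. That is correct.

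Third, a one-arm shift of 3.9 points is nearly twice the 2-point target, with missing controls no different at all. In that scenario the result is fairly robust. The smaller figures rest on an assumed 30% loss or an assumed smaller observed benefit. This too stands; the numbers show dependence on inputs and do not predict bias.

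Fourth, a reader might infer that missing data were ignored. They were not: the proportion missing and dropout rates are to be reported. Those figures can reveal unequal loss, but not what it does to the estimate. Adjustment for the stratification variables deals only with missingness that those variables explain.

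Last, the SAP is written largely in the past tense, so an addition may not count as prespecified. That limits its standing but not its use.

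**Conclusion.** The point holds in conditional form. It is certain that neither document states how a missing 3-month PHQ-9 enters the ITT regression, and that the complete case and per-protocol labels are merged. If missing scores are dropped, the only planned check omits the same people, about 96 of 480 at 20% attrition, and cannot show attrition bias.

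On the stated assumptions, a significant 2.0-point benefit is lost at a one-arm shift of about 3.9 points with 20% loss, or about 2.3 points with 30% loss in both arms. Across correlations of 0.3 to 0.7, the 20% figure runs from 3.3 to 5.0 if 6.6 is the SD of the 3-month score, and from 4.4 to 3.5 if it is a change-score SD; the documents do not settle which. The observed benefit, the correlation, the arm-specific losses and the shifts are all assumptions. The change should be made, but the primary model itself can stand.

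**What to change.** Keep the as-randomised adjusted linear regression as the primary analysis, and state its missing-data assumption: either observed 3-month scores under missing at random given arm, the randomisation factors and baseline PHQ-9, or a named imputation method.

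Add a delta-adjusted (tipping-point) sensitivity analysis of all randomised participants. It should shift missing outcomes separately in each arm over a grid and report the shifts at which the conclusion changes. If the primary analysis uses observed scores, it is already the complete case analysis, and the delta-adjusted analysis takes over as the check on attrition.

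Report missing 3-month PHQ-9 by arm with reasons, building on the missingness and dropout reporting already planned. Define any adherence-based per-protocol set separately from the complete case set. Fill in the placeholder drop-off percentage as an editorial correction.

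The cost is a paragraph of SAP text and a few model runs, with no new patients or procedures. There are two limits. An analysis added after the SAP of 8 August 2023 must be labelled with its date. And since a withdrawal request made before data aggregation "will result in all of the patient's files and data being destroyed" (Protocol 9.7), those participants can enter only as counts per arm, so the counts must be kept.

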7.5 Aims and Objectives

The primary aim of this project is to establish real-world efficacy that patient use of Wysa while waiting for treatment through the NHS mental health care pathway positively impacts well-being by comparing system users with standard services users.

The secondary aims of this project are:

1. To examine the feasibility of using Wysa to identify users at high risk of a mental health crisis and escalate them to further care;
2. To examine levels of user engagement with Wysa;
3. To evaluate patient acceptability of an autonomous early intervention supporting mental health services;
4. To complete a full health economic assessment of using Wysa for autonomous early intervention and triaging support;
5. To assess the potential for sustainable adoption of Wysa in mental healthcare pathways.

[figure not shown]

Figure 3. Wisconsin logic diagram

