8.3.4 Adherence

The study team will monitor the use of Wysa and assure the system is being used within designed parameters during the study.

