8.4.3.1 Quantitative data collection

The quantitative outcome measures will be delivered directly to patients through the Wysa app or by Qualtrics survey (e.g. for participants in the control group). Participants in both conditions will complete four questionnaires at baseline and 3-months post-randomisation (PHQ-9, GAD-7, EQ-5D-5L, and SF-12). Outcome measures have been chosen that will not be a significant burden for participants to complete; none of the questionnaires are longer than 12 items or expected to take more than a few minutes each to complete. Together, the questionnaires should take participants from 10 to 20 minutes to complete. Patient responses will be automatically uploaded to the iaptus electronic patient records using the Mayden Prism API. App use data will be automatically stored through the app.

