8.5.2 Other Data Analyses

Secondary analyses will include additional adjustment for factors showing possible imbalance at baseline and pre-planned exploratory analyses for differential effects of the intervention for different age groups, depression severity, and interaction (dose) of the Wysa app. Secondary analyses including adjustment for factors showing potential imbalance at baseline and pre-planned exploratory subgroup analyses for differential effects in a priori specified groups will be conducted using linear or logistic regression. For secondary analyses, where we have not specifically powered the study to detect statistical or clinical meaningful differences, we will report p-values but will focus on interpretation of 95% CI around estimates.

The qualitative semi-structured interviews will be evaluated using a thematic analysis.

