Statistical methods	20a	Statistical methods for analysing primary and secondary outcomes. Reference to where other details of the statistical analysis plan can be found, if not in the protocol			8.5
	20b	Methods for any additional analyses (eg, subgroup and adjusted analyses)			8.5
	20c	Definition of analysis population relating to protocol non-adherence (eg, as randomised analysis), and any statistical methods to handle missing data (eg, multiple imputation)			8.5
Methods: Monitoring					
Data monitoring	21a	Composition of data monitoring committee (DMC); summary of its role and reporting structure; statement of whether it is independent from the sponsor and competing interests; and reference to where further details about its charter can be found, if not in the protocol. Alternatively, an explanation of why a DMC is not needed			9.4, 9.5
	21b	Description of any interim analyses and stopping guidelines, including who will have access to these interim results and make the final decision to terminate the trial			9.8
Harms	22	Plans for collecting, assessing, reporting, and managing solicited and spontaneously reported adverse events and other unintended effects of trial interventions or trial conduct	SPIRIT-AI 22 Extension	Specify any plans to identify and analyse performance errors. If there are no plans for this, explain why not.	9.1
Auditing	23	Frequency and procedures for auditing trial conduct, if any, and whether the process will be independent from investigators and the sponsor			9.5
Ethics and Dissemination					
Research ethics approval	24	Plans for seeking research ethics committee/institutional review board (REC/IRB) approval			9.2
Protocol amendments	25	Plans for communicating important protocol modifications (eg, changes to eligibility criteria, outcomes, analyses) to relevant parties (eg, investigators, REC/IRBs, trial participants, trial registries, journals, regulators)			9.5
Consent or assent	26a	Who will obtain informed consent or assent from potential trial participants or authorised surrogates, and how (see Item 32)			8.3.3.2, 9.6

	26b	Additional consent provisions for collection and use of participant data and biological specimens in ancillary studies, if applicable			9.6
Confidentiality	27	How personal information about potential and enrolled participants will be collected, shared, and maintained in order to protect confidentiality before, during, and after the trial			9.7

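### The exploratory complete-case cohort is labelled per protocol although no document sets a condition on receiving or using Wysa, so its agreement with ITT would say nothing about non-use

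*Protocol*

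**What the plan says.** **Main comparison (Protocol 8.5.1).** "Comparative analyses will be conducted on an intention to treat basis, using linear or logistic regression, with adjustment for stratification variables".

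**Sensitivity cohort (Protocol 8.5.1).** After a paragraph on missing data and waiting-list drop-off, the section ends: "We will conduct exploratory sensitivity analyses in a complete case ('per protocol') cohort compared with the ITT analysis". Neither term is defined.

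**Adherence (Protocol 8.3.4).** "The study team will monitor the use of Wysa and assure the system is being used within designed parameters during the study". No parameter or minimum use is given.

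**Aim (Protocol 7.5).** The primary aim is worded as an effect of use: "patient use of Wysa while waiting for treatment through the NHS mental health care pathway positively impacts well-being by comparing system users with standard services". Section 8.2.5.1 likewise words the primary comparison as app users against patients on the standard pathway.

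**Data on use (Protocol 8.4.3.1).** "App use data will be automatically stored through the app".

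**Route of the PHQ-9 (Protocol 8.4.3.1).** Measures come through the app or by an online survey, and the control group is named only as an example of who gets the survey.

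**Analysis of use (Protocol 8.5.2).** The plan includes "pre-planned exploratory analyses for differential effects of the intervention for different age groups, depression severity, and interaction (dose) of the Wysa app".

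**SAP, Statistical methods.** Linear regression compares the two arms. No ITT, complete-case, per-protocol or use-based set is named.

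**The concern.** Complete case ordinarily means that the outcome was observed. Per protocol ordinarily means that the participant received the allocated intervention as planned. These are different selections, and the protocol applies both names to one cohort without an adherence condition.

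Non-use is foreseeable. Under 8.4.1.2 the intervention arm is emailed a download link, so opening the app is left to the participant, and 8.2.5.2 treats uptake and dropout as outcomes in their own right.

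A report that follows the plan could present an ITT estimate beside a similar per-protocol estimate. A reader would take the agreement as evidence that non-use made little difference. It would not be, because the same non-users can sit in both analyses. Since 8.5.1 names no imputation method, the ITT regression may be fitted to observed outcomes only, and then the two analyses could contain exactly the same people.

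**Working it through.** **1. Reproduce the planned size (background; the point is about definitions).** From Protocol 8.3.2.1 and 8.5.1: difference 2 points, SD 6.6, ratio 2:1, power 80%, two-sided 0.05. The normal formula gives 129 in the smaller arm and 387 in total. With the SD of 6.66 from the preliminary data it gives 131 × 3 = 393, the stated figure. With 480 randomised and 20% attrition, 480 × 0.8 = 384 are evaluable, split 128:256, and power is 79.9%.

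**2. Who is in the per-protocol cohort?** The only condition that can be read from 8.5.1 is that the 3-month PHQ-9 is present. Take a participant allocated to Wysa who never opens it:

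| 3-month PHQ-9 | In the cohort? | Consequence |
|---|---|---|
| Returned outside the app | Yes | A non-user is counted as per protocol |
| Not returned | No | The cohort moves towards app users against all responding controls |

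Section 8.4.3.1 permits the first row but does not guarantee it. The documents do not say which row will be common.

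**3. Size of the mislabelling.** Uptake is not stated, so I assume 80%, 60% and 40%. If every non-user returns a PHQ-9, non-users make up 1 − uptake of the per-protocol intervention group: 20%, 40% and 60%, or about 26, 51 and 77 of 128. If no non-user returns one, the share is 0.

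**4. What a complier average causal effect (CACE) would give.** ITT standard error, unadjusted: 6.6 × √(1/128 + 1/256) = 0.714. It is the same whichever arm is larger, so it is unaffected by the documents disagreeing on the direction of the 2:1 ratio (Protocol 8.3.2.1 favours usual care, the SAP favours the intervention). Approximately, CACE = ITT effect / uptake and its SE = 0.714 / uptake. This takes no control as using Wysa before 3 months; otherwise the divisor is the difference in activation between arms.

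| Assumed uptake | CACE SE | 95% half-width (1.96 × SE) |
|---|---|---|
| 80% | 0.89 | 1.75 |
| 60% | 1.19 | 2.33 |
| 40% | 1.79 | 3.50 |

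The ITT half-width is 1.96 × 0.714 = 1.40.

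**5. No gain in power.** Suppose use lowers PHQ-9 by 2 points and an unused offer does nothing. At 60% uptake the ITT effect is 0.6 × 2 = 1.2, with z = 1.2 / 0.714 = 1.68. The CACE is 2.0, with z = 2.0 / 1.19 = 1.68. The CACE changes the quantity estimated, not the strength of evidence.

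**6. What the CACE cannot repair.** Suppose the app is inert, non-users are 2 points worse for other reasons, and no non-user returns a PHQ-9. The complete-case contrast then shows a spurious benefit of (1 − uptake) × 2 = 0.4, 0.8 or 1.2 points at 80%, 60% or 40% uptake. Among those observed, uptake is 100%, so a CACE fitted to observed outcomes returns the same 0.4, 0.8 or 1.2.

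**The case against.** The strongest defence is that this is a slip of labelling. The sentence closes a passage about missing data, the per-protocol term is parenthetical, and the analysis is called exploratory. ITT is primary and untouched, and the SAP names no per-protocol analysis. All of that stands and limits the point. It does not remove it: a result issued under that label would still be uninformative on adherence.

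Three stronger readings are tempting, and the documents do not support them.

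- *That the effect of use is not analysed at all.* Section 8.5.2 plans an exploratory dose analysis, and app use is stored. What can be said is that this analysis has no dose metric, no model and no handling of confounding by engagement, and that controls receive the app only after the control period.
- *That the protocol fails its own reporting checklist.* Item 20c in Appendix 5 asks for a "Definition of analysis population relating to protocol non-adherence", but it offers an as-randomised analysis as an example, and the ITT statement in 8.5.1 meets that.
- *That lost power measures the defect.* If use is worth 2 points and non-users return the PHQ-9, ITT power is 61%, 39% and 20% at 80%, 60% and 40% uptake. That is ordinary dilution. It would be identical without the label, and step 5 shows that a CACE does not recover it.

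A fair objection to the remedy also stands. A CACE is one option among several, and counting any activation as receipt treats a single opening as full use. I prefer it to a use-selected set because it keeps the randomised comparison and needs no invented adherence rule for controls.

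**Conclusion.** The point holds in limited form. The planned per-protocol analysis has no condition on receipt or use, so it is a complete-case analysis under a misleading name. The share of non-users in its intervention group lies between 0 and 1 − uptake, depending on how far PHQ-9s are collected outside the app, which the documents leave open. Apart from that cohort, the effect of use rests on the unspecified dose analysis alone.

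No sample size, primary estimate or primary conclusion changes. The uptake values are assumptions. The standard errors also assume 384 evaluable participants, SD 6.6 and no covariate adjustment. This is a cheap improvement to a supportive analysis, not a flaw in the main comparison.

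**What to change.** 1. In Protocol 8.5.1, delete the per-protocol parenthesis, call the analysis complete case, and define it as having a 3-month PHQ-9. Carry the term into the SAP.
2. Keep ITT primary.
3. Add one supportive CACE by two-stage least squares: randomised arm as instrument, activation of Wysa within 3 months (from the app log) as treatment received, and the same covariates as the ITT model. The SAP is dated 8 August 2023 and mostly written in the past tense, so label the analysis by when it was specified.
4. Report activation against PHQ-9 return, with the route of collection, in the intervention arm. This shows which row of the table in step 2 applied. Read the CACE alongside the missing-outcome analysis.

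The cost is a few lines of text in the protocol and SAP, and one regression and one table on data already collected. The downsides to state are a wider interval (SE about 0.71/uptake, with uptake assumed until observed), no gain in power over ITT, the assumption that an unused offer has no effect, and no protection against bias if non-users do not return the PHQ-9.
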